5.2.2 PER-PROTOCOL POPULATION (PP)

The per-protocol population (PP) will include all ITT subjects who additionally meet all study eligibility criteria, have available study data for the study endpoint and do not have a major protocol violation that affects primary effectiveness and the propensity matched historical controls. Major protocol violations are described in section 6.4.

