Apparent Device malfunctions can be troubleshooted by site staff following provided materials, or by contacting sponsor for support, and should be recorded in patient files, along with initial date of occurrence, brief description, did it cause adverse events, whether damage is apparent. Malfunctions that impact essential performance, as defined in the Instructions for Use, should be recorded immediately and reported immediately to site-investigator. The site investigator may seek additional support from sponsor, but records in the EDC when a device is replaced due to malfunction, with date of replacement and start of malfunction. A device that doesn't maintain essential performance, as defined in the Instructions for Use, should be replaced (e.g. fails to power on, deploys without a fall, solid red light, blinking blue light). The site shall coordinate with the Sponsor Monitor for return and replacement, as needed.

All adverse events are to be evaluated for severity, relationship to product and whether they constitute an SAE, recorded in the EDC, to be reviewed by PI as described in section 8.4. PI continually monitors the enrolled study subjects for AEs and possible SAEs in the medical record.

PI should be notified immediately upon, Serious Adverse Event, fall event, or an AE that impacts utilization of the device.

Serious Adverse Events (SAE's) including status changes indicated in study subject medical records receive immediate attention of the Principal Investigator (PI) for consideration of device-related SAE. Serious AE (SAE) are to be reported to Sponsor and the IRB within 24 hours of the site becoming aware of the event. SAE notifications to the Sponsor are to be reported and completed via EDC.

Upon a fall event, site investigator is to initiate a Fall report, to gather evidence needed for the eventual adjudication of the Adverse Event, if required. Falls with Major Injury will be reviewed by the medical expert adjudicator as outlined in section 7.3. (Note, a Fall with Major Injury could *also* be considered a SAE for purposes of IRB reporting).

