10.4 Measures to Minimize Bias

Bias in assessments shall be minimized through using established assessment procedures under experienced investigators, in addition, all screening data and ongoing assessments will be reviewed by an independent observer to ensure integrity. The clinical investigator(s) will permit trial-related monitoring, audits, EMR review and

regulatory inspection(s), providing direct access to the trial site and to source data/documents on request.

11. Access and Verification of Source Data

Unique password-protected logins will be provided to the investigator and/or designee at each site to access source data and databases outside of the EMR, including the EDC platform and Tango Belt companion app for completion of the CRFs. Secure access to subjects' EMR data will be provided to site-authorized Sponsor monitor(s) for source data verification and quality purposes.

Source data verification will be performed for 100% of the subjects for enrollment criteria, primary endpoint, as well as adverse events. Regulations require that all data in the clinical investigation are captured in the patient's medical records (i.e., source documentation). All information generated by patient evaluations/examinations/interviews pertinent to the study are to be transferred by the clinical investigator (or designee) into the EDC platform via the CRF. Note that the FES-I questionnaire can be completed by the intervention subjects or administered by the investigator (or designee) directly using the Tango Belt companion app and will not require additional transcription into the EDC platform. All source documentation must be made available for inspection by the monitor, sponsor's staff or other authorized sponsor representative.

Source documents are documents on which information regarding subjects is first recorded. They are used to verify the existence of the subject and to substantiate the integrity of the data that are collected during a clinical trial. Investigator subject files generally are the basis of source document information. This includes but is not limited to original subject files, operative reports, progress notes, clinic records, and original recordings. Any additional information relevant to the study should be included in source documents. In particular, any deviations from the study protocol or procedures should be recorded.

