5.2.3 ADHERENCE POPULATION

The adherence population includes all subjects in the PP population excluding those subjects who were not actually wearing Tango Belt when the primary effectiveness endpoint was experienced.

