6.4 PROTOCOL DEVIATIONS

Subjects with such non-compliance will be determined prior to database lock. Major protocol deviations will be summarized in the CSR. This summary will include the number and percent of subjects (overall and by site) with each deviation type.

Major deviations in this study include, but not limited to the following:

- Inadequate or delinquent informed consent
- Inclusion/exclusion criteria not met
- Unreported serious adverse events or fall event

SAP: COP-0001
Active Protective Technologies, Inc

- Materially inadequate record keeping
- Intentional deviation from protocol, Good Clinical Practice, or regulations by study personnel

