7.2 PRIMARY EFFECTIVENESS ANALYSIS

The primary effectiveness endpoint for this study is the proportion of subjects experiencing major hip injuries due to falls, as reported at the 180-day visit and will be presented for the Tango Belt and control groups using the ITT and adherence populations.

The proportion of subjects experiencing major hip injury due to falls is defined as the total number of subjects who experience a major hip injury due to a fall divided by the total number of subjects.

The primary effectiveness hypotheses are:

$$\begin{array}{l} H_0 \colon \pi_T \ \geq \ \pi_C \\ H_1 \colon \pi_T \ < \pi_C \end{array}$$

where π_T and π_C are the proportion of subjects experiencing major hip injuries due to falls in the Tango Belt and control group, respectively.

The null hypothesis (H_0) for this endpoint states that the true proportion of subjects using Tango Belt and experiencing major hip injuries due to falls is greater than or equal to the true proportion of subjects in the control group who experience major hip injuries due to falls. The alternative hypothesis (H_1) states that the true proportion of subjects using Tango Belt and experiencing major hip injuries due to falls is less than the true proportion of subjects in the control group who experience major hip injuries due to falls.

The proportion of major hip injuries by treatment group will be presented along with a 95% confidence interval using the Clopper-Pearson method. H_0 will be tested at a one-sided 0.025 level of significance using a logistic regression analysis to compare treatment groups while controlling for propensity score.

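### The per-protocol rule can drop a belt subject for an unreported fall or serious adverse event, an outcome-dependent, one-arm exclusion that carries into the supportive adherence comparison

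*Combined protocol and SAP*

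**What the plan says.** SAP 5.2.2 defines PP as ITT subjects who meet eligibility, have endpoint data and "do not have a major protocol violation that affects primary effectiveness and the propensity matched historical controls". It adds: "Major protocol violations are described in section 6.4".

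SAP 6.4 gives that list, which largely repeats protocol 14.3. One item is "Unreported serious adverse events or fall event". On timing, 6.4 says: "Subjects with such non-compliance will be determined prior to database lock". It does not say that whoever decides is blinded to outcome. The blinded statistician in SAP 7.1 is assigned only the propensity score modelling and design.

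SAP 5.2.3 builds on PP: "The adherence population includes all subjects in the PP population", less those injured while not wearing the belt. SAP 7.2 presents the primary endpoint for the Tango Belt and "control groups using the ITT and adherence populations". SAP 5.2 removes the matched controls of any belt subject who is excluded.

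Reporting duties are prospective. Protocol 8.1 defines adverse events for subjects receiving the device and counts every fall as one. Protocol 8.3 states: "Serious AE (SAE) are to be reported to Sponsor and the IRB within 24 hours of the site becoming aware of the event". Control data are extracted afterwards from the medical record (SAP 5.1). Protocol section 11 provides a way for missed events to surface: "Source data verification will be performed for 100% of the subjects for enrollment criteria, primary endpoint, as well as adverse events".

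**The concern.** A per-protocol exclusion should not depend on the outcome. This one can. Consider three belt subjects:

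- One has no fall or serious adverse event. This subject can never meet the item and always stays.
- One has a fall with major hip injury that the site reported. This subject stays and counts as an event.
- One has the same injury, unreported by the site and found later in the medical record. On a natural reading this is a major deviation that bears on primary effectiveness, so the subject and the verified event leave PP.

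A control with the same injury has no report to miss, so no control event can be removed this way. A verified endpoint event could thus be deleted from one arm of a comparison shown next to the primary result, because of a lapse in site paperwork. Changing the off-belt rule in SAP 5.2.3 would leave this route open.

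**Working it through.** **Inputs from the documents.** Belt and control numbers are 94 and 188 at the interim and 188 and 376 at the final look, before attrition (SAP 2, 4). Control risk is 15% (SAP 4). Target protection is 80% at the interim and 60% at the final look, with one-sided alpha 0.025, 1:2 allocation and Pocock spending (SAP 4, 4.1). **Not in the documents:** the share *f* of belt hip injuries that would be removed, so a range is shown.

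**Step 1: the plan's own figure.** Pocock spend at half information is 0.025 × ln(1 + (e − 1) × 0.5) = 0.0155. The usual two-proportion formula for 3% against 15%, one-sided alpha 0.0155, 80% power and 1:2 allocation gives 82 belt subjects, or 94 with continuity correction. This is the stated 94. At the final look, 6% against 15% at nominal alpha 0.0147 with the correction gives 183, within 3% of the stated 188. So 15% behaves as the risk over the 6-month follow-up, although SAP 4.1 calls it annual. It is used that way below.

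**Step 2: sensitivity to single events.** Protection = 1 − (belt rate ÷ 0.15).

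| Look | Belt events / subjects | Apparent protection |
|---|---|---|
| Interim, none removed | 3/94 = 3.19% | 78.7% |
| Interim, one removed | 2/93 = 2.15% | 85.7% |
| Final, none removed | 11/188 = 5.85% | 61.0% |
| Final, one removed | 10/187 = 5.35% | 64.3% |
| Final, three removed | 8/185 = 4.32% | 71.2% |

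The starting counts are the expected ones: 94 × 0.03 ≈ 3 and 188 × 0.06 ≈ 11.

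**Step 3: a belt with no effect.** If only hip injuries are removed, the apparent belt rate is p(1 − f) ÷ (1 − p·f). With p = 0.15:

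- f = 10%: 0.135 ÷ 0.985 = 13.7%, an apparent 8.6% reduction.
- f = 25%: 0.1125 ÷ 0.9625 = 11.7%, an apparent 22.1% reduction.

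Simulation at 188 and 376 subjects, dropping two controls with each removed belt subject, gives a one-sided false-positive rate of about 2.4% at f = 0. At f = 10% it is 5.2% with a pooled z test and 5.4% with a Wald logistic test. At f = 25% it is about 18%. If 15% were truly annual (7.5% over 6 months), the Wald figures are 2.0% at f = 0 and 3.8% at f = 10%.

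**Step 4: do the dropped controls compensate?** No. They are matched on age, mobility, sex and falls in the past year, not on outcome, so their expected rate stays at 15%.

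**Step 5: other unreported events.** The item also covers falls and serious adverse events without hip injury. Dropping those subjects removes non-events and raises the belt rate. Assume that 15% of belt subjects have a hip injury and a further 35% only another fall or serious event, with shares u and v removed. The belt rate is then 0.15(1 − u) ÷ (1 − 0.15u − 0.35v).

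- u = v = 20%: 0.12 ÷ 0.90 = 13.3%, an apparent 11% benefit.
- u = 5%, v = 20%: 0.1425 ÷ 0.9225 = 15.4%, so the belt looks worse.
- No bias when 0.85u = 0.35v, that is v ≈ 2.4u.

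**The case against.** The strongest reply is that nothing confirmatory is at risk, and this stands. SAP 6.3 ties the primary analysis to imputed ITT data, SAP 7.3 puts the secondary endpoints on ITT, and ITT has no deviation exclusion. Section 7 names no PP comparison, so the only route is the adherence result. A reader might infer that the trial's type I error is inflated; the documents do not support that.

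Second, SAP 5.2.2 requires a violation that affects primary effectiveness. Once a late-found event is entered and adjudicated, the endpoint is right, and one could argue that nothing was affected. That reading is possible, but the text does not state it. The opposite reading is at least as natural, and under it the qualifier tends to pick out hip injuries, the events that matter most.

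Third, *unreported* is undefined, and few hip injuries should go missing. By the protocol's own description (2.2) these are serious injuries. Protocol 7.3 takes falls, emergency visits and admissions from the medical record at 90 and 180 days, and 8.3 adds continual record monitoring. This stands and argues for a small *f*. A reader might take removal of 20% or 30% of events as likely; nothing in the documents suggests it.

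Fourth, the direction is not fixed. A reader might infer that the rule always flatters the belt. Step 5 shows that it need not.

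**Conclusion.** The point holds as a flaw in a supportive analysis. SAP 5.2.2 read with 6.4 permits an exclusion that depends on outcome, can arise only in the belt arm, and passes through PP into the adherence result. Dropping the matched controls does not offset it, and the plan states no blinding for the decision.

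The likely size is one or a few subjects. That matters because few belt events are expected: one removal shifts final-look protection by about three percentage points, and removing a tenth of hip injuries roughly doubles the false-positive rate of that comparison under no effect. These figures assume that 15% is the 6-month risk, that only hip-injury subjects are removed, and that the test is unadjusted. Removing other unreported events as well shrinks the bias and, in the illustration, reverses it above about 2.4 times the miss rate for hip injuries. The separate off-belt exclusion in SAP 5.2.3 may have the larger effect on the same population.

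**What to change.** In SAP 5.2.2 and 6.4, state that:

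1. an unreported or late-found serious adverse event or fall is summarised as a site deviation but does not remove the subject from the PP or adherence population;
2. the event, once verified in the medical record and adjudicated, is counted;
3. deviations that exclude from PP are limited to those that do not depend on a fall or serious adverse event, such as invalid consent or eligibility not met at baseline;
4. those exclusions are decided before database lock by someone blinded to endpoint data. The blinded statistician in SAP 7.1 could take this on.

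The cost is a few sentences, with no new data, visits or subjects. The supportive results may look slightly less favourable.

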5.2.3 ADHERENCE POPULATION

The adherence population includes all subjects in the PP population excluding those subjects who were not actually wearing Tango Belt when the primary effectiveness endpoint was experienced.

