4.1 INTERIM ANALYSES

The study will incorporate a group sequential design (GSD) in which an interim analysis will be performed to detect an 80% protective effect of the Tango Belt at 80% power. If a significant difference is found between the prospective Tango Belt subjects and historical controls at the interim analysis, the study will be stopped, and the Tango Belt deemed superior to SOC alone. If not, sample size reestimation will be completed, and enrollment will continue until a final sample size is reached to detect a 60% protective effect of the Tango Belt at 80% power and a 5% total level of significance.

Following the steps from section 4, we assumed subjects were followed for an average of 6 months, an annual fall-with-major-hip-injury rate of 15%, and sufficient historical control subjects to allow 1:2 allocation of subjects to treatment and control. This would require 134 subjects in the prospective Tango Belt group and 268 subjects in the historical control group at the interim analysis using the Pocock alpha-spending function as well as accounting for 30% attrition. At the end of the study (should the higher effectiveness target not be achieved at interim analysis), 268 total subjects would be required in the prospective Tango Belt group and 536 subjects would be in the historical control group.

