5.2 Intervention Population

Propensity score matching (described in section 7.1) will be used to match each treatment group subject with two subjects from the historical control group. If a subject from the treatment group is not included in any of the analysis populations described below, the historical control subjects they matched to using propensity scores will also not be included in any analysis comparing groups.

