6.3 METHODS FOR WITHDRAWALS AND MISSING DATA

All practical monitoring and follow-up steps will be taken to ensure complete and accurate data collection. Since endpoints are assessed at the 180-day visit, it is anticipated that there will be approximately 30% attrition. Given the disproportionately high rate of death and other loss-to-follow up reasons within this population, multiple imputation approaches will be carried out for missing primary endpoint data on the ITT population. The primary effectiveness analysis will be performed on data that has the primary outcome multiply imputed.

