6.3.1 MULTIPLE IMPUTATION

Prior to propensity score matching, the intervention group may have missing information on the primary endpoint (i.e. major hip injury due to a fall), primarily due to premature withdrawal from the study.

At the time of the final analysis, if more than 20% of data is missing for the primary endpoint reported at the 180-day visit, then the primary endpoint will be multiply imputed and the analysis from section 7.2 will be repeated using both observed and multiply imputed data.

For the multiple imputation, a total of 50 imputed datasets will be calculated (Graham et al.). Fully conditional specification (FCS) logistic regression will be used to impute missing major hip injury due to a fall status (primary endpoint) using the baseline covariates of age, sex, ethnicity, race, mobility level (Independent, Limited Assist, Supervision, Extensive Assist, or Total Dependence), BIMS Score, and FES-I score.

The analysis for the primary endpoint will be carried out utilizing 50 datasets and then results will be combined using PROC MIANALYZE in SAS to obtain one overall test of significance.

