7 EFFECTIVENESS ANALYSES

Given that subjects in the two comparison groups (Tango Belt vs. SOC) are not randomized and thus may not have balanced baseline characteristics, Propensity Score (PS) matching will be carried out to adjust for measured baseline confounders prior to any statistical test(s) comparing treatments on effectiveness endpoints at the interim and final analysis.

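### SAP 5.2.3 selects the adherence population on the outcome, so the between-group comparison that SAP 7.2 presents on it is biased toward benefit

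*Combined protocol and SAP*

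**What the plan says.** - **Who is removed.** SAP 5.2.3 starts from the per-protocol (PP) set and defines the adherence population by "excluding those subjects who were not actually wearing Tango Belt when the primary effectiveness endpoint was experienced".
- **What happens to controls.** Under SAP 5.2, when a belt subject is left out, "the historical control subjects they matched to using propensity scores will also not be included in any analysis comparing groups". The controls' own outcomes play no part.
- **Where the set is used.** SAP 7.2 says that the primary endpoint "will be presented for the Tango Belt and control groups using the ITT and adherence populations". It does not rank the two, and it then describes one test of H0 without naming a population.
- **What points to ITT.** SAP 6.3 places imputation of the primary endpoint on ITT and adds: "The primary effectiveness analysis will be performed on data that has the primary outcome multiply imputed". SAP 5.2.2 admits to PP only subjects who "have available study data for the study endpoint". SAP 7.3 names ITT alone for the secondary endpoints.
- **What is left open.** SAP 6.3.1 makes imputation conditional and dates it: "At the time of the final analysis, if more than 20% of data is missing for the primary endpoint". SAP 7 requires matching "prior to any statistical test(s) comparing treatments on effectiveness endpoints at the interim and final analysis", so it covers both looks. SAP 4.1 says that on a significant interim difference "the study will be stopped, and the Tango Belt deemed superior to SOC alone", and names no analysis population.

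**The concern.** The rule is called adherence, but it acts through the outcome. Take two belt subjects with the same low wear. The one injured while the belt is off is removed, and the one not injured stays and counts as a success. Controls face no equivalent filter, so events leave one arm only.

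Off-belt injuries are to be expected. Protocol 5.3 allows the belt to come off for bathing, dressing, charging and on request. A subject can pass run-in with 1 hour on 9 of 14 days, which is 9 of 14 × 24 = 336 hours (2.7%). Neither protocol 5.4 nor the deviation list in SAP 6.4 sets a minimum wear after that. The run-in figure is a floor, not expected wear.

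At stake is how the primary endpoint of a non-randomised, historically controlled study will read. A result that favours the belt by construction would stand beside the ITT result under the heading of the primary analysis.

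**Working it through.** **Inputs**
- p, the control risk: 15% (SAP 4, observed proportion). SAP 4.1 labels 15% an annual rate with 6 months of follow-up, so 7.5% is run as well.
- Sizes before attrition: 94 belt and 188 control subjects at the interim, 188 and 376 at the final (SAP 2). One-sided alpha 0.025 (SAP 4). Pocock-type spending (SAP 4.1).
- w, the share of belt-arm injuries that would occur on the belt if it had no effect. **This is an assumption.** The documents do not give it, and hours worn do not determine it. Range used: 0.5 to 0.95.

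**Step 1. Reproduce the plan's interim size.** The Pocock spend at half the information is 0.025 × ln(1 + (e − 1) × 0.5) = 0.0155 (z = 2.157). With 15% against 3% (an 80% reduction), 80% power and 1:2 allocation, the two-proportion formula gives 81.5 belt subjects, and 93.5 with continuity correction. That rounds up to the SAP's 94 and treats 15% as the 6-month proportion.

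**Step 2. Expected relative risk when the belt does nothing.** Each belt subject is injured on the belt (probability pw), injured off it (p(1 − w), removed) or uninjured (1 − p, kept). The retained belt-arm risk is pw/(1 − p(1 − w)). The control risk stays p. So

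RR = w / (1 − p(1 − w)).

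Example: w = 0.75, p = 0.15 gives 0.75 / (1 − 0.0375) = 0.78.

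| w | RR, p = 15% | RR, p = 7.5% |
|---|---|---|
| 0.95 | 0.96 | 0.95 |
| 0.90 | 0.91 | 0.91 |
| 0.75 | 0.78 | 0.76 |
| 0.50 | 0.54 | 0.52 |

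In counts, 188 × 0.15 = 28.2 belt injuries are expected, and at w = 0.75 about 28.2 × 0.25 = 7 of them are removed.

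**Step 3. Does dropping matched controls repair this?** Only slightly, and only if the matching covariates predict injury. With two equal strata at assumed risks of 5% and 25% (400,000 simulations, exact matching on stratum), RR is 0.96, 0.92, 0.79 and 0.56 for the same w.

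**Step 4. Does the set estimate the effect while worn?** For a true while-worn reduction E, the adherence reduction is 1 − w(1 − E)/(1 − p(1 − w)). With E = 60%, w = 0.75, p = 15%: 1 − 0.30/0.9625 = 69%. The ITT reduction is 0.75 × 60% = 45%. The adherence figure exceeds the while-worn effect itself whenever w < 1.

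**Step 5. False positives, only if this set were used to decide H0.** Exact enumeration with no belt effect, each removed belt subject taking two controls out regardless of outcome, unadjusted pooled z test:

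| w | Final 188/376, nominal 0.025: p = 15% / 7.5% | Interim 94/188, level 0.0155: p = 15% / 7.5% |
|---|---|---|
| 1 | 2.3% / 2.2% | 1.35% / 1.1% |
| 0.90 | 5.6% / 4.2% | 2.65% / 1.8% |
| 0.75 | 17% / 10% | 6.9% / 3.8% |
| 0.50 | 62% / 36% | 27% / 12% |

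At w = 1 no one is removed, so that row is also the ITT result. The SAP's estimated propensity score, nearest-neighbour matching and logistic model are not modelled.

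**The case against.** **ITT already decides.** This largely stands. SAP 6.3 bases the primary analysis on imputed data and does the imputing on ITT. The adherence set sits inside PP, which needs an observed endpoint, so an imputed analysis cannot be the adherence analysis. The imputation trigger is more than 20% missing, and SAP 6.3 expects about 30% attrition, so on the plan's own expectation it is met at the final analysis. SAP 7.2 says only that results are presented for both sets.

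A reader might therefore go too far and infer that the trial's type I error is inflated, or that the interim stop could rest on the adherence set. The documents do not support that. Nothing gives adherence a deciding role, and SAP 4.1 speaks of the belt subjects and the historical controls as groups. What remains is a missing label: ITT is implied but not stated, and the imputation text that implies it is tied to the final analysis.

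**The size is unknown.** This stands. Protocol 5.3 prescribes wear up to 24 hours a day, and protocol 2.3 reports wear above 12 hours. If w is 0.90 to 0.95, the RR is 0.91 to 0.96.

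**Low wearers may be dropped anyway.** Possibly: PP removes major violations, and the SAP 6.4 list is not exhaustive. But low wear is not on it.

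**The wording could cut the other way.** PP includes matched controls, who never wore a belt. Read literally, SAP 5.2.3 could remove every control with an event and leave a control proportion of zero. That cannot be intended, but it shows that the rule needs limiting to belt subjects.

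**Conclusion.** Wrong as written, and should be fixed. On the evident reading, the between-group adherence comparison favours the belt in expectation whenever some belt-arm injuries occur off the belt. A single realised sample could still fall either way. The direction needs only w < 1. The size depends on the assumed w: at p = 15% and no belt effect, the expected spurious reduction runs from about 4% (w = 0.95) to 46% (w = 0.5). The comparison cannot be read as the belt's effect, nor as its effect while worn.

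On the implied reading that ITT decides H0, error control is untouched and the damage is limited to a misleading supportive estimate of the primary endpoint. The false-positive rates in Step 5 describe a use of this set that the documents point away from. They show why it should have no deciding role, not what the trial will do.

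**What to change.** 1. In SAP 5.2.3 and 7.2, replace the between-group adherence comparison with a description within the belt arm: injuries on the belt, injuries off it, and airbag deployments. Alternatively, define adherence by recorded wear over a fixed window, regardless of outcome. Either way, limit the criterion to belt subjects and label the result supportive, with no part in stopping or in the claim.
2. In SAP 7.2 and 4.1, state that H0 is tested on ITT at both the interim and the final analysis, with all on-belt and off-belt events kept, whether or not imputation is triggered.

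The cost is SAP wording. The supportive result may look less favourable. No new data, subjects or follow-up are needed.
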